10.3 Other study parameters

In order to identify clinical factors possibly associated with of ischemic response, simple and logistic regression analyses will be applied. Covariates that show possible associations with ischemic responses ($P<0.10$) will be conceived as possible predictors. However, our sample size will be too small to identify independent predictors. If our approach will be successful, identification of independent predictors will be studied in a larger patient group.

In order to identify neuronal properties that are possibly associated with ischemic responses, simple logistic regression analyses will be applied as well.

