4. STUDY POPULATION

4.1 Population (base)

Ten patients with ischemic stroke will be included in this study. These patients should have clearly documented cerebral infarcts, confirmed by MRI or CT imaging. Patients will be included during follow up, at approximately six to eight weeks from stroke onset, or later.

hiPSCs from five age-matched control subjects from our repository will be used as controls.

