4.4 Sample size calculation

Sample size calculation is hampered by lack of data. A sample size of ten patients and five controls is based on feasibility considerations: cell lines, culturing, and measurements of 15 subjects are possible within 2 years and provide a first estimation of the feasibility of the objectives.

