8.1.2 Secondary study parameters

Electrophysiological responses to simulated 'cerebral ischemia', i.e. reduction of oxygen and glucose levels in the medium at eight to ten weeks after plating, as described previously.¹⁴

- Percentage reduction in network activity, functional connectivity, and synaptic responses (i.e. network responses to electrical stimulation of one electrode).
- Speed of reduction in network activity, functional connectivity, and synaptic responses.
- Extent of restoration of network activity, functional connectivity, and synaptic responses after restoration of oxygen and glucose levels.

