8.3 Study procedures

Procedures in patients

All patients with acute brain infarcts will be admitted to a stroke unit to receive diagnosis and treatment as usual, as described in national and local stroke unit protocols. Standard CT or MRI, CT-angiography, CT-perfusion, and measures of neurological impairment and functional recovery are collected in the context of current care.

Patients will be informed about the study after admission on the stroke unit or at the time of follow up by the treating physician. If the patient gives permission, the treating physician will contact the research coordinator or study nurse. The research coordinator or study nurse will then contact the patient and provide additional information, both orally and written. The patient will be able to read the information carefully, discuss with family and ask questions. Patients will have at least one week to consider participation. . Inclusion will take place at the time of follow up, approximately six to eight weeks after infarction.

After oral and written informed consent, 30cc of venous blood in heparin anticoagulant (3x10cc) will be collected, handled, and stored according to local guidelines. Blood samples from patients will be collected during routine follow up at the hospitals outpatient department. Blood samples will be collected during routine blood sampling, if possible. If not, there will be one additional puncture. There will be no additional hospital visit.

Procedures in blood samples

Blood samples will be transported to University of Twente, CNPH lab, for further work-up and analysis. In short, we will generate iPSCs lines by exposing lymphoblast to reprogramming factors using a non-integrating episomal plasmid system to acutely express the Yamanaka reprogramming factors.^{15,16} hiPSC clones will be validated for pluripotency and genomic integrity through a standardized battery of quality control tests. iPS cells will be directly derived into excitatory and inhibitory neurons as published previously.¹⁷ Physiological ratios of excitatory and inhibitory neurons will be grown on Multiwell-MEAs for non-invasive, continuous recording of network functioning through extracellular electrodes. In parallel, cultures plated on coverslips will be fixed in 4% paraformaldehyde in 0.1M PBS at pH 7.4 for immunocytochemical staining (Figure 1). Staining protocols are available on request.

[figure not shown]

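### Logistic regression is the only method named for relating neuronal properties to ischemic responses, but those responses are continuous and no cut-point is defined

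*Protocol*

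**What the plan says.** Protocol section 8.1.2 lists the ischemic responses. The first group is "Percentage reduction in network activity, functional connectivity, and synaptic responses", the second is "Speed of reduction in network activity, functional connectivity, and synaptic responses", and the third is how far the same three quantities recover once oxygen and glucose are restored. All are measured on a continuous scale. No responder definition, threshold or binary version of a response appears in the protocol.

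Section 10.3 has two paragraphs on relating these responses to other factors:

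- For clinical factors, "simple and logistic regression analyses will be applied". Covariates with P<0.10 are then treated as candidate predictors only. The protocol concedes that the sample cannot establish independent ones.
- For neuronal properties, "simple logistic regression analyses will be applied as well". No second method is named.

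On numbers, section 4.1 states "Ten patients with ischemic stroke will be included in this study" and "hiPSCs from five age-matched control subjects from our repository will be used as controls". Section 4.4 adds that "A sample size of ten patients and five controls is based on feasibility considerations". Section 10.3 does not say whether the controls enter these regressions.

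**The concern.** The named model does not fit the scale of its outcome. Simple logistic regression models the probability of a yes/no outcome, so the analysis in the second paragraph of 10.3 cannot be run until someone splits each response into high and low. The protocol gives no basis for that split, and it could be chosen after the data are seen.

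This differs from a detail that a protocol may leave to the SAP. The protocol does choose a method, and the choice conflicts with its own endpoints. A SAP that followed 10.3 would inherit the mismatch, and one that did not would depart from the protocol.

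At stake is one half of the tertiary objective in section 2, the link between ischemic responses and neuronal properties. With so few subjects, the information lost by dichotomising is a sizeable share of what there is, and the usual large-sample P values of a logistic model cannot be trusted.

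**Working it through.** The protocol states no power, effect size or standard deviation, so there is no figure of its own to reproduce. The check is a simulation.

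**Inputs from the protocol.** n = 10 patients, or 15 subjects with the five controls (4.1). Continuous responses (8.1.2). Threshold P<0.10 (10.3), stated for clinical covariates and taken here to apply to neuronal properties too.

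**Assumptions not in the protocol.** One predictor and one response per subject, bivariate normal with correlation rho; a median split of the response (5/5 at n = 10, 7/8 at n = 15); two-sided tests. Because rho is unknown, a range of 0.5, 0.7 and 0.8 is shown. There were 10,000 runs per setting and 20,000 under no association, so the Monte Carlo standard error of a power figure is at most √(0.25/10,000) = 0.5 percentage points.

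**Tests compared.**

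- Linear: t = r√(n−2)/√(1−r²), on n−2 degrees of freedom.
- Logistic, Wald: |estimate/standard error| > 1.645. A separated data set has no finite estimate and counts as not significant.
- Logistic, likelihood ratio (LR): 2(l₁−l₀) > 2.71. A separated data set reaches the maximum, 2·10·ln 2 = 13.9 at n = 10, and counts as significant.
- Size-corrected LR: the cut-off is raised until 10% of null data sets are rejected. This gives 3.63 at n = 10 and 3.28 at n = 15.

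**Results (% of runs with P<0.10; last row of each block: % separated).**

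| n | Analysis | No association | rho 0.5 | rho 0.7 | rho 0.8 |
|---|---|---|---|---|---|
| 10 | Linear | 9.9 | 46 | 79 | 93 |
| 10 | Logistic, Wald | 1.7 | 5 | 8 | 9 |
| 10 | Logistic, LR | 15 | 40 | 65 | 82 |
| 10 | Logistic, LR size-corrected | 10 | 30 | 54 | 72 |
| 10 | Complete separation | 0.8 | 4.5 | 11 | 19 |
| 15 | Linear | 10.4 | 63 | 93 | 99 |
| 15 | Logistic, Wald | 6.9 | 32 | 57 | 65 |
| 15 | Logistic, LR | 13 | 50 | 81 | 93 |
| 15 | Logistic, LR size-corrected | 10 | 43 | 75 | 90 |
| 15 | Complete separation | 0.04 | 0.8 | 3.5 | 7 |

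**Exact check.** With no association, complete separation at a 5/5 split has probability 2/C(10,5) = 2/252 = 0.8%, as simulated.

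**Power kept at n = 10 after size correction.** 30/46 = 0.65, 54/79 = 0.68 and 72/93 = 0.77 of the linear power. The Wald test keeps 5/46 = 0.11, 8/79 = 0.10 and 9/93 = 0.10. At n = 15 the Wald test keeps 32/63 = 0.51, 57/93 = 0.61 and 65/99 = 0.66.

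**Sensitivity to the split.** If the response is split 3/7 at n = 10, separation rises to 7%, 15% and 23% at the same correlations (3,000 runs).

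**The case against.** The strongest reply is that this is an exploratory, tertiary analysis in a study sized for feasibility, that hits are treated only as candidates, and that the protocol itself defers independent predictors to a larger study. That stands, and it limits the severity. It does not excuse the mismatch, because the admission concerns independent predictors and not a univariable model that does not fit its outcome.

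A second reply is that the first paragraph of 10.3 is acceptable. Where it says "simple and logistic regression analyses will be applied", *simple* beside *logistic* most naturally means simple linear regression. This also stands, so the first paragraph needs clarification only. One may add that the second paragraph is a slip for the same pair of methods. That is possible, but as written it names logistic regression alone.

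Three stronger readings are tempting, and the documents do not support them:

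- *Logistic regression loses nearly all power.* This is true only of the Wald test at n = 10. The protocol names no test, and a size-corrected likelihood-ratio test keeps about two thirds to three quarters of the linear power. If the controls are included, n is 15 and the Wald test keeps about half to two thirds.
- *The model often has no finite solution.* For a continuous predictor and a median split, separation is below 1% with no association and 4.5–19% at rho 0.5–0.8. It becomes frequent with an unbalanced binary predictor. For a 3/7 predictor against a 5/5 response, a zero cell has null probability 2·C(5,3)/C(10,3) = 20/120 = 17%, and simulation gives 36–68% at rho 0.5–0.8. Such predictors belong to the clinical factors, where linear regression may already be planned. None of the neuronal properties in 8.1.3 is defined as binary.
- *One subject value would be analysed as 15 observations.* Section 8.3 says that "cultures plated on coverslips will be fixed in 4% paraformaldehyde" in parallel to the recorded cultures, so a property can be linked to a response only through the subject or batch. However, 10.3 does not state a network-level regression, and the unit of analysis may properly be left to the SAP.

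**Conclusion.** The point holds for the second paragraph of section 10.3. Logistic regression is the only method named there, all responses are continuous, and no cut-point exists. This follows from the text alone, without any simulation.

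The size of the consequence rests on the stated assumptions of normality, a median split, one value per subject and rho between 0.5 and 0.8. On those assumptions the loss is material at n = 10 and smaller, but still present, at n = 15. The P<0.10 screen is unreliable whichever usual test is chosen. At n = 10 the Wald test rejects far below its nominal 10% under no association, and the likelihood-ratio test rejects above it.

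The severity is should-fix. The descriptive primary outcome and the secondary comparisons are untouched. A reader might infer that the tertiary analysis would mostly return infinite or empty results; the figures show a weaker and less reliable analysis, not a void one.

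**What to change.** In the second paragraph of 10.3, replace logistic regression by simple linear regression of the subject-level continuous response on the subject-level neuronal property. Spearman correlation is an alternative where the data are clearly not normal. Report the slope with its 95% interval, not only whether P<0.10 is met.

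In the first paragraph, state that *simple* means simple linear regression and that it is used for the continuous responses.

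If a binary response is really intended, define its cut-point before the data are seen and use a penalised or exact logistic method.

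The cost is a rewording of one section. No additional subjects, cultures or measurements are needed.

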10.4 Interim analysis (if applicable)

Not applicable

11. ETHICAL CONSIDERATIONS

11.1 Regulation statement

This study will be conducted according to the principles of the Declaration of Helsinki (7th revision, Fortaleza, 2013) and in accordance with the Medical Research Involving Human Subjects Act (WMO) and other guidelines.

11.2 Recruitment and consent

Consecutive patients who meet the inclusion criteria will be asked for informed consent at the stroke unit or out-patient department of participating hospitals by the treating doctor, coordinating / principle investigator, or dedicated study nurse. The patient information letter and informed consent form are attached to this file. There will be sufficient time for consideration, at least half a day.

11.3 Objection by minors or incapacitated subjects (if applicable)

Not applicable: minors or incapacitated patients will not be included

11.4 Benefits and risks assessment, group relatedness

No relevant additional risks are expected for patients or controls.

11.5 Compensation for injury

Since no relevant additional risks are expected, we request exemption from the requirement of a liability insurance for patients and controls.

11.6 Incentives (if applicable)

Not applicable

12. ADMINISTRATIVE ASPECTS, MONITORING AND PUBLICATION

12.1 Handling and storage of data and documents

All patients will receive a study number by which all data will be coded. The study coordinator and the principal investigators will have access to the source data, if necessary. The code will be safeguarded by the study coordinator. The study data will be stored digitally and saved for 15 years.

12.2 Monitoring and Quality Assurance

Not applicable

12.3 Amendments

Relevant amendments will be notified to the METC that gave a favourable opinion. Non-substantial amendments will not be notified to the accredited METC and the competent authority, but will be recorded and filed by the sponsor.

12.4 Annual progress report

The sponsor/investigator will submit a summary of the progress of the trial to the accredited METC once a year. Information will be provided on the date of inclusion of the first subject, numbers of subjects included and numbers of subjects that have completed the trial, serious adverse events/ serious adverse reactions, other problems, and amendments.

12.5 Temporary halt and (prematurely) end of study report

The investigator/sponsor will notify the accredited METC of the end of the study within a period of 8 weeks. The end of the study is defined as the last patient's last visit. Of note, neuronal cultures will be kept and studied thereafter.

The sponsor will notify the METC immediately of a temporary halt of the study, including the reason of such an action.

In case the study is ended prematurely, the sponsor will notify the accredited METC within 15 days, including the reasons for the premature termination.

Within one year after the end of the study, the investigator/sponsor will submit a final

study report with the results of the study, including any publications/abstracts of the study, to the accredited METC.

12.6 Public disclosure and publication policy

Publications will be by both principle investigators and engaged PhD or master students, if applicable. The collaborating investigators will adhere to the CCMO guideline on publication, as published on <https://www.ccmo.nl/publicaties/publicaties/2002/03/15/ccmo-notitie-publicatiebeleid>. Details on the publication policy are kept in a separate agreement.

13. STRUCTURED RISK ANALYSIS

Not applicable

